### **Summary of Analytic Plan:**

We will use graphical and numerical summaries to describe the outcomes at each assessment point. If distributional assumptions for particular statistical procedures are violated, appropriate transformations will be made or non-parametric tests will be used. All primary and secondary analyses will follow the intent-to-treat principle; all participants will be analyzed in the group to which their clinic was assigned irrespective of their post-randomization behavior, and all participants will be analyzed using multiple imputation techniques. Hypothesis-driven comparisons will be made with control of the type I error rate at 0.05 (two-sided).

**Preliminary Analysis.** We will examine data for out of range values. Descriptive statistics will be generated regarding practice characteristics such as size (small, medium, large), practice type (hospital-based practice, Federally Qualified Health Center, neighborhood health center), and patient mix (pediatrics, adult/pediatrics) to help to understand the sample as well as the generalizability of study findings. We will determine whether there are differences at baseline between the eMPI and eUC providers and patients in demographics and background characteristics. This will include analogs of t-tests (or Wilcoxon rank sum tests) for continuous variables and chi-square (or Fisher's Exact) tests for categorical variables adjusted by generalized estimating equation (GEE) methods for the clustering induced by providers within clinics.

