**Aim 2. To determine whether consistent use of eMPI leads to both short- and long-term improvements in clinical outcomes.** In this Aim, we will compare the change from baseline to each of the follow up (FU) time points (i.e., 3, 6, 9, and 12 months) in number of SFDs between eMPI and eUC patients using intent-to-treat principles. We will employ the generalized linear model (GLM) with identity link function for this comparison. The analysis model is of the form  $EY_{ij} = \alpha + \beta I_i + \sum \gamma_j T_{ij} + \sum \delta_j I_j T_{ij}$ , where for subject  $i$   $Y_{ij}$  is the number of SFDs for at time  $j$ ,  $I_i$  denotes group indicator for eMPI group (vs. eUC), and  $T_{ij}$  is the indicator for time at FU $j$  evaluation (vs. baseline). The regression coefficient  $\delta_j$  corresponding to the group-by-time interaction term estimates the difference in average change of SFDs at FU $j$  evaluation vs. baseline, comparing eMPI to eUC groups, and thus represents the effect of intervention on the SFDs. We will use generalized estimating equations (GEE) methodology to account for within-subject correlation due to multiple assessments for the same subject as well as the within-provider and within-practice correlations due to cluster sampling. We will also determine whether or not the corrective actions taken mediates the effect of intervention on outcomes; we will use the test of joint significance of the 2 paths involving a potential mediator, which best balance Type I error and statistical power. A variable  $M$  will be declared a mediator only if both the test of the regression coefficient of the explanatory factor  $X$  on the mediator and the test of the coefficient of the mediator on the outcome variable  $Y$  controlling for  $X$  are significant at level alpha = 0.05, 2-tailed. This approach allows for partial mediation which we fully expect to occur. In subsequent analyses we will estimate the indirect path effect with 95% confidence intervals using the asymmetric distribution of products method. Further exploration of causal mediation will

follow the methods of Imai et al. We will also examine whether the effect of intervention on SFDs is mediated by provider competencies, provider/caregiver communication or caregiver self-efficacy.

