Missing data: Every effort to retain participants in the study will be exerted in order to avoid bias due to attrition. For those individuals who refuse continued participation, we will document reasons for study discontinuation and Rubin's multiple imputation method with 5 repeated imputations will be employed to impute the missing endpoint for conducting the intent-to-treat analysis.

**Power Analysis.** With a recruitment of 512 participants at baseline, we anticipate a final sample of 460 participants with complete data for the primary analysis assuming no more than 10% attrition at 12 month evaluation. This estimate of attrition rate is conservative based on our prior experience. To account for the intra-cluster correlation due to cluster sampling, we estimate that an intra-provider correlation coefficient is no greater than 0.03 from our prior studies. Although the intra-practice correlation coefficient should be smaller than intra-provider correlation coefficient, we conservatively used the same value (i.e., 0.03). Under the above assumption, with 230 participants per group, we will be able to provide 80% power to detect a standardized effect size of  $\geq 0.29$  in change of number of SFDs. Even if actual attrition is greater than we expect (e.g., 15%), the detectable standardized effect size will only increase slightly to 0.30. Further, as we will impute missing data using informative covariates for the primary analyses, the power to detect such effects will be  $>80\%$ .

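### Five imputations leave a borderline symptom-free-day result dependent on the random seed, and the unspecified imputation model should be written to carry practice clustering

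*Combined protocol and SAP*

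**What the plan says.** The Summary of Analytic Plan states that "all participants will be analyzed using multiple imputation techniques", with two-sided testing at 0.05. The number of imputations appears once, in the Missing data paragraph under Aim 2, where Rubin's method "with 5 repeated imputations will be employed to impute the missing endpoint for conducting the intent-to-treat analysis".

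The content of the imputation model is described only in the Aim 2 Power Analysis: "we will impute missing data using informative covariates for the primary analyses". No section names practice, provider or matched pair as a term in it. No section gives a seed or a check on Monte Carlo error.

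The Aim 2 analysis model is more explicit. It uses GEE to account for repeated measures and for the "within-provider and within-practice correlations due to cluster sampling".

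**The concern.** Five imputations are usually defended on efficiency, and on that ground the defence holds. Efficiency describes the average over many runs, whereas the trial will report one run. With few imputations the pooled estimate, and so z and p, moves from seed to seed. With no seed stated, two analysts who follow the plan exactly could reach opposite conclusions on a borderline SFD result. The plan gives several places for this to happen: a group-by-time coefficient at each of four follow-ups, and a mediation rule that depends on tests at 0.05.

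The second issue is conditional. Practices are randomized and the GEE is built around their correlation, but the imputation step does not mention clustering. If it were run without practice, imputed values would carry no within-practice correlation, and the standard error would be somewhat too small.

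**Working it through.** **Inputs from the documents.** 512 children enrolled; 10% attrition, with 15% as the pessimistic case; intra-practice correlation 0.03, which the plan chose as a conservative value (all Aim 2). 18 participating practices, 22 planned (Subjects and Setting). M = 5 imputations.

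**Assumptions not in the documents.** Missingness at random, equal practice sizes, a single endpoint in place of the repeated-measures GEE, and the strength of any predictor.

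**The plan's own figures.** 512 × 0.90 = 460.8, which agrees with the planned 460. The detectable effect of 0.29 does not follow from the stated inputs: (1.96 + 0.842) × √(2/230) = 0.261 without clustering, and 0.344 with 18 practices (design effect 1 + (460/18 − 1) × 0.03 = 1.737). That is a separate matter and nothing below depends on it.

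**Formulas.** Let m be children per practice, f the missing fraction and ρ the practice correlation. Take the variance of an arm mean in units of σ²/n, and impute without practice or predictor:
- within-imputation variance W = 1 + (m − 1)ρ(1 − f)²
- between-imputation variance B = f/(1 − f)
- total T = W + B
- true variance V = [1 + ((1 − f)m − 1)ρ]/(1 − f)
- seed-to-seed SD of z ≈ √((B/T)/M)

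**18 practices, m = 512/18 = 28.44, ρ = 0.03**

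| f | W | B | T | B/T | SD of z, M = 5 | SD of z, M = 50 |
|---|---|---|---|---|---|---|
| 0.10 | 1.667 | 0.111 | 1.778 | 0.0625 | 0.112 | 0.035 |
| 0.15 | 1.595 | 0.176 | 1.771 | 0.0996 | 0.141 | 0.045 |

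With 22 practices the M = 5 values are 0.116 and 0.146.

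**Efficiency loss at M = 5.** About (B/T)/5: 1.2% at 10% missing and 2.0% at 15%.

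**Spread of p.** A result at p = 0.05 has z = 1.96. Its 95% range over seeds is 1.96 ± 1.96 × 0.112, or p from 0.029 to 0.082, at 10% missing. At 15% missing the range is 0.025 to 0.092.

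**Result truly at p = 0.04.** Here z = 2.054, which is 0.094 above 1.96.
- M = 5: 0.094/0.112 = 0.84, so about 20% of seeds miss significance; 0.094/0.141 = 0.67, so about 25%.
- M = 50: about 0.4% and 1.8%.

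Simulation with Rubin's t reference, with and without a predictor, gave 14% to 34% at M = 5, 1% to 15% at M = 20, 0% to 5% at M = 50, and under 1% at M = 100.

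**Standard error if practice is omitted.** The ratio of reported to true standard error is √(T/V).
- 10% missing: V = 1.931, and √(1.778/1.931) = 0.960.
- 15% missing: V = 1.995, and √(1.771/1.995) = 0.942.
- With 22 practices: 0.965 and 0.950.

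The shortfall is therefore about 4% to 6%, and a nominal 5% test runs at about 5.9% to 6.5%. With an assumed predictor correlated 0.6 with the endpoint, simulation gave a shortfall of 2.5% to 4%.

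At ρ = 0.01 the formula gives √(1.333/1.384) = 0.981 and √(1.375/1.449) = 0.974, that is 1.9% and 2.6%. Simulation gave about 1.5%, and 0.3 to 0.6 points with a predictor correlated 0.5.

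**Simulated standard-error ratios** (ρ = 0.03, 18 practices, 1,500 data sets per row, no predictor)

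| Missing | M | Complete data | Without practice | Random practice effect |
|---|---|---|---|---|
| 10% | 5 | 1.033 | 0.992 | 1.031 |
| 10% | 20 | 1.003 | 0.966 | 1.004 |
| 15% | 5 | 1.015 | 0.956 | 1.022 |
| 15% | 20 | 1.008 | 0.961 | 1.026 |

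Relative to complete data, omitting practice costs about 4% at 10% missing and 5% to 6% at 15%. A random practice effect brings the ratio back to about the complete-data level.

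**The case against.** Five imputations are not an error. Rubin's (1 + 1/M) factor already puts the Monte Carlo variance into the standard error, so a reader who infers that the planned test is invalid goes too far. The exposed zone is also narrow. With a critical value of 2.12 (t on 16 df), about 5% of null trials and 17% of trials at 80% power fall within 0.3 of it. In simulation, two seeds disagreed in 20% to 30% of such data sets, so roughly 0.05 × 20% = 1% to 0.17 × 30% = 5% of trials are affected. All of this stands, and it sets the size of the point. A pre-stated seed would end disagreement between analysts, but it makes one arbitrary draw reproducible and does not stabilise it. More imputations do.

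A reader might also infer that the plan leaves practice out and that its standard error is therefore too small. The documents do not support that: they are silent on practice and do not exclude it, and they list practice and provider characteristics among the covariates. Nor can all the excess type I error be charged to imputation. In one set of simulations the complete-data standard-error ratio was already 0.967 and 0.953, which is small-sample sandwich bias with 18 clusters. Omitting practice took it to 0.942 and 0.922 and added 0.5 to 0.8 points of type I error. The correlation of 0.03 is itself an upper bound.

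Finally, the general statement on multiple imputation, and the reference to primary analyses in the Aim 2 power text, might suggest that the primary outcome is at risk. The Aim 1 result comes from a permutation test on paired clinic proportions, and the sentence fixing five imputations stands under Aim 2. It does not affect the Aim 1 test.

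**Conclusion.** The point holds as a low-cost improvement to a secondary analysis. At M = 5 the seed-to-seed SD of z is about 0.11 to 0.15, and a result truly at p = 0.04 is lost under roughly 14% to 34% of seeds. At M = 50 the figures are about 0.035 to 0.045 and 0% to 5%. Results well away from 0.05 are not affected.

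The standard-error part is conditional on an imputation model run without practice. The shortfall would then be about 2.5% to 6% at a correlation of 0.03 and below 3% at 0.01. Type I error would be roughly 5.3% to 6.5%, part of it small-sample sandwich bias that is present without imputation. The defect in the text is an unspecified imputation model, not a wrong one. These sizes rest on the assumptions listed with the inputs.

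**What to change.** In the Aim 2 Missing data paragraph, replace 5 with at least 50 imputations, state the seed in advance and commit to reporting the Monte Carlo error. Specify that the imputation model contains arm, SFD at all other visits and a random practice effect, so that it matches the clustering in the GEE analysis.

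Practice should not enter as fixed indicators. In simulation at a correlation of 0.03 that made the standard error about 4% to 8% too large relative to complete data.

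The cost is one SAP sentence and minutes of computing. It should be settled before unblinded analysis, because a later choice of M or model on a borderline result would look driven by that result.

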## B. Subjects and Setting

Outpatient practices (n=22) that are part of Montefiore Health System will participate in the study (see Letter of Support). These 22 practices are located throughout the Bronx, NY, represent different practice types, and have participated in several of our prior studies (Table 3). Though there were initially 22 proposed outpatient practices, two practices were closed, two practices (FCC-B and FCC-C) were combined as a single site given that they serve patients in the same facility, and one practice was excluded given no pairing available, resulting in a total n=18 participating outpatient practices. The number of children with asthma across practices (N=10,109) of whom we estimate ~ 50% (N=5,000) to have persistent or uncontrolled asthma is sufficient to meet our sample size needs. A subset of 512 children will be recruited over 4 years (~128 participants each year) to obtain clinical outcomes data that are not in the EHR.

Table 1. Primary Care Practices*					
Site	Practice Type	Provider Type	# 2-12yr olds in practice	# 2-12yr olds with asthma	# visits for 2-12yr olds with asthma
Astor Avenue	NHC	Pediatrics	3,075	576	1,012
Bronx East	NHC	Pediatrics	4,775	884	1,516
Burke Avenue	NHC	Pediatrics/Family MD	1,102	117	196
Castle Hill	FQHC	Family MD	814	97	135
CFCC	FQHC	Pediatrics	5,791	1,144	1,824
CHCC	FQHC	Pediatrics	4,658	1,332	2,488
Co-op Bartow Ave	NHC	Pediatrics	2,485	634	1,059
Eastchester	NHC	Pediatrics	1,350	325	703
FCC - B	Hospital Clinic	Pediatrics	3,671	684	1,028
FCC - C	Hospital Clinic	Pediatrics	3,470	805	1,300
FHC	FQHC	Family MD	1,739	339	606
Grand Concourse	NHC	Pediatrics/Family MD	3,133	540	868
Grand UCC	NHC	Pediatrics/Family MD	2,950	235	262
HIP Cross County	NHC	Pediatrics/Family MD	3,058	272	385
MAP-8	Hospital Clinic	Pediatrics	2,935	631	1,551
Marble Hill	NHC	Pediatrics/Family MD	1,143	186	294
University Avenue	FQHC	Pediatrics/Family MD	1,697	344	645
Verde Clinic	NHC	Family MD	359	78	146
Wakefield	NHC	Pediatrics	354	309	600
West Farms	FQHC	Family MD	954	215	368
White Plains Road	NHC	Pediatrics/Family MD	1,204	174	273
Williamsbridge	FQHC	Family MD	1,059	188	308
TOTAL	-	-	51,776	10,109	17,567

FQHC=Federally Qualified Health Center; NHC=Neighborhood Health Center. \*Number of patients seen between 1/1/14-12/31/14

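### The Aim 2 detectable effect of 0.29 (0.30 at 15% attrition) does not follow from the plan's inputs, which give 0.33 to 0.35 with 22 practices and 0.34 to 0.37 with 18

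*Combined protocol and SAP*

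**What the plan says.** The Summary of Analytic Plan sets the error rate: "Hypothesis-driven comparisons will be made with control of the type I error rate at 0.05 (two-sided"). Hypothesis 2a, on improvement in SFDs, is one of the hypotheses it covers.

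The Power Analysis under Aim 2 starts from 512 children, expects 460 with complete data after 10% attrition, and says that "with 230 participants per group, we will be able to provide 80% power to detect a standardized effect size of" 0.29 or more in the change in SFDs. On clustering it says "we estimate that an intra-provider correlation coefficient is no greater than 0.03 from our prior studies". For the practice level, where a smaller value is expected, it says "we conservatively used the same value (i.e., 0.03"). At 15% attrition, "the detectable standardized effect size will only increase slightly to 0.30". It closes by saying that "as we will impute missing data using informative covariates for the primary analyses, the power to detect such effects will be" above 80%.

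That paragraph gives no alpha, number of practices, cluster size or design effect. Study Design randomizes 22 practices. Subjects and Setting reports closures, a merger and an exclusion, "resulting in a total n=18 participating outpatient practices".

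**The concern.** With 460 children in 22 practices, each practice supplies about 21. At an ICC of 0.03 that inflates the variance by about 60%. A detectable effect of 0.29 is only 11% above the 0.261 that would apply with no clustering at all, so it leaves room for a variance inflation of only about 23%. The stated inputs and the stated result therefore do not fit together.

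SFDs are the plan's main clinical outcome. If the design has nearer 60-69% power than 80% at 0.29, a null Aim 2 result could be read as stronger evidence against an effect of that size than the design can supply.

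**Working it through.** **Inputs.** Two-sided 0.05 (Summary of Analytic Plan). From the Aim 2 Power Analysis: 80% power, N = 460 (230 per group), N = 435 at 15% attrition (512 × 0.85), and ICC 0.03 at provider and practice level. Practices: k = 22 (Study Design) or 18 (Subjects and Setting). Equal practice sizes are assumed, and 0.03 is applied to the change score, because the stated effect is on the change and "we will compare the change from baseline to each of the follow up (FU) time points" is the planned comparison.

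**Formulas.** When the provider and practice ICCs are equal, the nested design effect reduces to DE = 1 + (N/k − 1) × 0.03. Then SE = √(4·DE/N) in standard deviation units. The detectable effect is (1.960 + 0.842) × SE by the normal approximation (z), or comes from the noncentral t on k − 2 degrees of freedom.

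**Worked case, 22 practices.** N/k = 20.91; DE = 1 + 19.91 × 0.03 = 1.597; SE = √(4 × 1.597/460) = 0.1179; detectable effect = 2.802 × 0.1179 = 0.330 (z), or 0.347 (t, 20 df).

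| N | k | DE | Detectable effect, z to t | Plan states | Power at the stated effect, z to t |
|---|---|---|---|---|---|
| 460 | 22 | 1.597 | 0.330 to 0.347 | 0.29 | 69% to 65% |
| 460 | 18 | 1.737 | 0.344 to 0.367 | 0.29 | 66% to 60% |
| 435 | 22 | 1.563 | 0.336 to 0.353 | 0.30 | 71% to 66% |
| 435 | 18 | 1.695 | 0.350 to 0.373 | 0.30 | 67% to 62% |

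Most of the gap is already there with 22 practices. Going to 18 adds 0.014 (z) to 0.020 (t). By z, 80% power at 0.29 would need about 738 complete children in 22 practices, or 959 in 18.

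**Attempts to reproduce 0.29 and 0.30.**

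- No clustering: 2.802 × √(4/460) = 0.261.
- Clustering by provider only (about 200 providers, 2.3 children each): 0.266.
- All 512 children analysed, 22 practices: 0.320.
- One-sided 0.05, 22 practices, z: 0.293 and 0.298. Both figures match, but the plan is two-sided.
- Two-sided 0.05 at 70% power, 22 practices, z: 2.484 × 0.1179 = 0.293 and 2.484 × 0.1199 = 0.298. Both match, but the plan says 80%.
- Two-sided z with a smaller practice ICC: the implied DE is (0.29/0.2612)² = 1.232. Both figures match for an ICC of 0.011 to 0.014 (22 practices) or 0.009 to 0.011 (18), but the plan says 0.03.

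Several routes lead to the stated figures and each conflicts with something the plan states, so the cause cannot be identified from the documents.

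**Imputation sentence.** Take the best case, all 512 children observed. DE is 1.668 (22) or 1.823 (18), and power at 0.29 is 72% to 68% or 68% to 63%. Imputing missing values cannot be expected to do better than having them.

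**Unequal practice sizes.** Enrolment goals follow each practice's asthma count. The 22 counts in Table 1 have a coefficient of variation of about 0.73. With DE = 1 + ((1 + 0.73²) × N/k − 1) × 0.03, the detectable effect at N = 460 becomes about 0.36 to 0.38 (22) or 0.38 to 0.41 (18, assuming the same variation).

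**The case against.** The best counter-argument is that the plan never says which variable the 0.03 describes. If it is the ICC of SFDs at a single visit, the ICC of the change is 0.03 × (1 − c)/(1 − r). Here c is the correlation of practice effects over time and r is a child's baseline-to-follow-up correlation. With c = 0.8 and r = 0.5 the ICC of change is 0.012, and 22 practices give 0.291 and 0.297 by z, matching both stated figures at two-sided 0.05. This possibility stands, but c and r are assumptions that the plan does not give. Over c from 0.5 to 0.9 and r from 0.3 to 0.5, the z result runs from 0.27 to 0.33 (22) or 0.28 to 0.34 (18). On this reading 0.29 is possible but cannot be verified.

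The effect might also be standardized by the SD of SFDs rather than of the change. The detectable effect is then multiplied by √(2(1 − r)), and r of about 0.605 with 22 practices gives 0.293 and 0.299. This is a less natural reading of an effect stated on the change, and r is again not given.

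Two further points are fair. The plan calls 0.03 an upper bound, so 60-69% is power at that bound rather than expected power; but the paragraph says 0.03 was the value used. The lower ends of the power ranges rest on t with k − 2 degrees of freedom, which the plan does not specify for its GEE analysis. By z alone, power at 0.29 is 69% (22) and 66% (18), still well short of 80%.

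**Conclusion.** The concern holds. On the plan's own inputs the detectable effect is 0.330 to 0.347 with 22 practices and 0.344 to 0.367 with 18, against 0.29 stated. At 15% attrition it is 0.336 to 0.353 or 0.350 to 0.373, against 0.30. Power at 0.29 falls short of 80% by about 11 to 15 percentage points with 22 practices and 14 to 20 with 18. The statement that imputation brings power above 80% fails on the same inputs.

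This rests on equal practice sizes, on 0.03 applying to the change score, and on no gain from pair matching. The power paragraph counts no such gain, and the Aim 2 model has no pair term. Unequal sizes would widen the gap; a smaller ICC for the change score would narrow or close it, but the plan states none.

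The consequence is limited. Aim 2 is secondary, no estimate or test changes, and the Aim 1 permutation test is unaffected. The paragraph should still be corrected, because its power figure is one that the stated inputs do not deliver.

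**What to change.** Rewrite the Aim 2 power paragraph for 18 practices:

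- State the alpha and sidedness, number of practices, design effect, the variable to which the 0.03 refers, and the SD used to standardize the effect.
- At two-sided 0.05 and ICC 0.03 on the change score, give the detectable effect as about 0.34 (0.37 with t on 16 df), and 0.35 (0.37 with t) at 15% attrition.
- If a smaller ICC for the change score is intended, give its value and justify it, then recalculate.
- Delete the sentence that imputation makes power exceed 80%.
- Note that unequal practice sizes would raise the detectable effect further.

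The cost is the wording of one paragraph and a less favourable stated figure. Design, data collection and analysis stay as they are.

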**Randomization:** Prior to participant enrollment, each practice will be matched into 11 pairs based on size of the practice and provider type (Table 1). Practices will then be randomly selected within each pair as an eMPI or a eUC site. Practices will join in 4 waves over the course of 4 years (4-6 practices/year). Each practice will remain in the study for 24 months and receive \$500 donation to thank them for participation.

**Inclusion Criteria:** The criteria listed below will apply to ~5,000 children from eMPI and eUC practices. We will obtain a waiver of consent to be able to review EHR data by practice.

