**Aim 3. To evaluate the process of program implementation:** In order to evaluate the potential for dissemination of this primary care intervention, we will report specific summary measures recommended by the RE-AIM framework. We will compare the provider-level proportion of visits with corrective actions taken by the eMPI providers to that of eUC providers using the same analytic approach stated in Aim 2 (Reach). We will evaluate the impact of eMPI on guideline-based corrective actions and symptoms (*Effectiveness*). We will qualitatively describe problem solving progress that occurs in each practice as part of process of improvement, by coding the specific barriers that arise during implementation and are collected by clinic champions, and the solutions that eMPI practices identify (*Adoption*). We will report consistency with which participants in the intervention arm receive the protocol through EHR data, practice observations of the process of implementation and data collected from OW contacts with participants. Additional measures of implementation of eMPI include 1) caregivers' completion of severity/control assessments at the visit; 2) provider and caregiver receipt of prompts; 3) providers' documentation of asthma discussion (*Implementation*). We will use provider survey responses to evaluate the extent to which each intervention component was continued or modified post-study and sustained effects on the primary outcome (*Maintenance*). Using EHR records of 5,000 children across all four waves of translation, we will determine if eMPI practices will (a) reach successively higher levels of guideline-based care, (b) achieve that level more quickly, and (c) sustain use of guidelines for 18 months. The analytic approach to address this will involve a statistical model with the main effect of intervention condition, time (which represents the level of Implementation), and the indicators of waves (which will allow us to evaluate sustainability), plus all the two-way and three-way interactions. We expect to see specific three-way interaction effects involving trends in rates of guideline-based care over 24 months, with an ever steeper linear increases and less pronounced downturns seen from wave to wave, in eMPI practices vs. eUC. Guideline-based care is intended to ensure that children receive needed services in a more timely fashion. We will examine patterns of utilization by children in both groups using the EHR, including adherence to clinic visits, specialty referrals, emergency and in-patient care, and OW referrals.

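### The Aim 3 wave model does not say how practice-level variation enters, although each arm-by-wave cell holds only 2-3 practices; the practice or pair should be the unit and the wave comparison labelled descriptive

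*Combined protocol and SAP*

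**What the plan says.** Under Summary of Analytic Plan, Aim 3, the wave question is addressed as follows: "Using EHR records of 5,000 children across all four waves of translation", the plan will determine whether eMPI practices (a) "reach successively higher levels of guideline-based care", (b) get there more quickly and (c) sustain guideline use for 18 months. The tool is "a statistical model with the main effect of intervention condition, time (which represents the level of Implementation), and the indicators of waves", "plus all the two-way and three-way interactions". The expected result is stated: "We expect to see specific three-way interaction effects involving trends in rates of guideline-based care over 24 months". No practice, provider or pair effect, GEE or unit of analysis is named for this model.

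Clustering is named elsewhere. The Preliminary Analysis uses GEE for providers within clinics, Aim 1 permutes within pairs, and Aim 2 uses GEE for provider and practice. Aim 3 borrows the Aim 2 approach for the Reach comparison only.

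On the number of practices, Subjects and Setting (Randomization) says "each practice will be matched into 11 pairs based on size of the practice and provider type" and "Practices will join in 4 waves over the course of 4 years (4-6 practices/year". The same section reports later losses, "resulting in a total n=18 participating outpatient practices".

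**The concern.** A practice belongs to one arm and one wave. Any comparison of the arm effect across waves is therefore a comparison between small groups of practices, however many children's records lie behind it. With four waves of 4-6 practices split between two arms, each cell holds 2-3 practices.

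Two or three practices can differ from another two or three by chance, in level or in trend. If the standard errors come from the count of records, those differences can be significant when nothing has improved from wave to wave. At stake is the claim that the programme gets better with successive waves, which bears on dissemination. Claim (a), on levels, rests on arm-by-wave. Claims (b) and (c), on pace and maintenance, rest mainly on the three-way term.

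**Working it through.** **The plan's nearest figure.** The wave model has no stated power or error rate. The primary test does: 11 pairs, 25 points, SD of pair differences 0.20. Non-centrality = 1.25 × √11 = 4.15, and a paired t-test with 10 df gives power 96.1%, which agrees with the stated figure of more than 95%.

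**Inputs from the documents**
- SD of pair differences: 0.20 (stated upper bound) and 0.142 (mock data). If pair members are independent (assumption), the SD per practice is 0.20/√2 = 0.141 and 0.142/√2 = 0.100.
- Intra-practice correlation 0.03, given for symptom-free days only. At a proportion of 0.5 it would mean a practice SD of √(0.03 × 0.25) = 0.087.
- Eligible visits per practice-quarter: 17,567 × 0.5 / 22 / 4 ≈ 100, applying the plan's 50% share to visits.
- Baseline plus 3-monthly extraction to 24 months: 9 time points.

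**Assumptions.** Pairs join together, as 2/2/2/3 (9 pairs, 18 practices) or 3/3/3/2 (11 pairs, 22 practices). The arm effect is the same in every wave, so any wave finding is false. Practice level SD runs from 0 to 0.141 and practice trend SD over 24 months from 0 to 0.14. The documents give no trend SD.

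**1. Listed terms, visits treated as independent** (3-df tests at 5%; 1,000 runs per setting, Monte Carlo SE at most 1.6 points):

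| Arm-by-wave: practice level SD | False positives |
|---|---|
| 0 | about 5% |
| 0.02 | 36-38% |
| 0.05 | 87% |
| 0.087 | 97% |
| 0.10 | 96-98% |
| 0.141 | 99% |

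| Arm-by-wave-by-time: practice trend SD | False positives |
|---|---|
| 0 (practices differ in level only) | 4-6% |
| 0.02 | 7-8% |
| 0.05 | 25-26% |
| 0.10 | 64-66% |
| 0.14 | 81-83% |

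**2. Aim 2 GEE carried over, no small-sample correction.** Both interactions reject in 42-48% of runs with 18 practices and 32-37% with 22. A separate check with 40,000 runs on practice-level summaries gives 44% (9 pairs) and 34% (11 pairs) for the 3-df test, and about 20% for wave 4 versus wave 1 alone. The robust variance in each cell is estimated from only 2-3 practices.

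**3. Partial repairs.** A pair term alone leaves arm-by-wave at 86-99%. A practice intercept alone leaves the three-way test at 26-28% (trend SD 0.05) or 68-69% (trend SD 0.10), so practice-by-time variation is needed too.

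**4. Practice or pair as the unit.** Practice means or slopes, with F on 3 and 10 df (18 practices) or 14 df (22), give 4-6.5% in all settings. A linear trend over 9 pair differences (7 df) gives 4.9%.

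**5. Precision of the corrected analysis.** Wave 4 (3 pairs) versus wave 1 (2 pairs), with 9 − 4 = 5 df:
- Pair SD 0.20: SE = 0.20 × √(1/2 + 1/3) = 0.183; half-width = 2.571 × 0.183 = 0.47.
- Pair SD 0.087 × √2 ≈ 0.12: SE ≈ 0.112; half-width ≈ 0.29.

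For a linear trend over 9 pairs the sum of squares of wave number is 12. The rise detectable at 80% power is 13 points per wave at SD 0.142 and 19 at SD 0.20, or about 40-57 points from wave 1 to wave 4.

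**The case against.** The plan lists mean-model terms and is silent on the error structure. Silence does not mean that records will be treated as independent, and the authors account for clustering in their other main comparisons. This stands, so the documents do not support saying that chance differences will be declared learning. It does not rescue the model, because the obvious default, the Aim 2 GEE, also fails with 2-3 practices per cell.

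The outcome is defined at clinic level, and Data Storage and Confidentiality says the waiver data are obtained at clinic level. The model may therefore be fitted to practice-by-quarter rates. The record-level rates in step 1 would then not apply as they stand. Repeated rates from one practice would still share its level and trend, and the plan does not say how that is handled.

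A reader might infer that the expected three-way interaction would appear by chance about half the time. A design effect of 1 + (277.8 − 1) × 0.03 = 9.30, for 5,000/18 = 277.8 children per practice, gives an error rate of 52% in a 1-df test. But that is for a between-practice mean, with a correlation given for another outcome. Constant practice differences drop out of time trends, and the three-way test is then at 4-6%. Nor does the absence of a pair term, as such, explain the problem (step 3).

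The consequence is limited. Aim 3 carries no numbered hypothesis, the plan gives no decision rule for this model, and the primary permutation test is separate.

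**Conclusion.** The concern holds in a limited form. The plan does not state how practice-level variation enters a model whose key factors vary only between practices, with 2-3 per cell. On the listed terms with independent records, the arm-by-wave test is badly inflated at any practice SD of 0.02 or more. The three-way test is inflated only if practices differ in trend, by an amount that depends on an assumed SD. Uncorrected GEE by practice gives 32-48% for both. These figures rest on the assumed wave allocation, about 100 visits per practice-quarter, and practice SDs taken from the power section or assumed.

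Even analysed correctly, the wave comparison is imprecise: the half-width in level is 29-47 points, against a planned main effect of 25. It can describe but not establish learning across waves. This is worth correcting before analysis, but it does not affect the primary result.

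**What to change.** Amend Aim 3 to make the practice the unit of the wave analysis, or the matched pair if its members join in the same wave, which the SAP should confirm. For each pair compute the eMPI minus eUC difference in:

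1. level at the end of consolidation, for claim (a);
2. rate of rise from baseline to that point, for claim (b);
3. change from then to month 24, for claim (c).

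Relate each to wave with practice- or pair-level degrees of freedom, for example a linear trend over the 9 pairs with 7 df. Report estimates with confidence intervals and label the comparison descriptive. Do not rest the learning claim on the record-level three-way test. If a regression on records is kept, it needs practice and practice-by-time variation with small-sample degrees of freedom. Practice fixed effects are not an option for arm-by-wave, because practices are nested in arm and wave.

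The cost is SAP wording; the quarterly extractions already planned supply the data. The downside is a visibly imprecise wave inference. A linear trend would also miss a non-linear pattern across waves, so the pair differences should be shown by wave as well.
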